#### **4.4.3 Phase 2: Treatment (1 Year)**

##### 1 Month, 3 Month, 6 Month and 1 Year Visit (+/- 7 Day Window)

- Continuance Criteria: patients will be released from study participation for the following reasons:
  - non-compliance with study procedures
  - development of a medical condition or taking a medication which would affect the study outcome, as covered in the exclusion criteria
  - disease progression or unacceptable toxicity of study drug, as assessed by the investigator
  - pregnancy
  - withdrawal of patient consent
  - protocol violation
  - lost to follow-up
  
- Review of Medical Records, if applicable
  
- Medical/Dental History update
  
- Concomitant Medications update
  
- Urine Pregnancy Test (if female of child bearing potential)
  
- Oral Cavity Assessment (soft & hard tissues, extraoral, head & neck)
  
- Physical Exam
  
- Clinical Laboratories (at 3 month, 6 month and 1 year visit)
  
- Genetic Testing for Blood (at 1 year visit)
  
- Genetic Testing for the Tumor (at 1 year visit)
  
- Vital Signs (blood pressure, heart rate, temperature)
  
- Panoramic Radiograph
  
- Volumetric CT Scan (at 6 month and 1 year visit)

- Skin Examination for NBCCS-associated KCOT patients at 6 month and 1 year visit
- Photographs of Skin Lesions, if applicable
- Compliance with Study Drug
  - Compliance with study drug will be checked by counting the capsules that were returned to the site versus the capsules that were administered to patient at the end of the last visit. Any discrepancy will be documented in the patient's chart and in the drug accountability log. Study reminders regarding compliance will be reviewed with the patient in order to maximize the proper use of the study drug.
- Study Drug Dispense until next visit
- Adverse Events

Upon discharge from the clinic, specific instructions will be given to patients regarding the use of the medication, as well as adequate study drug supplies until their next visit. Patients will be instructed the following:

- Not to donate blood or blood products while receiving GDC-0449 and for at least 24 months after the last dose of the study drug.
- Not to get pregnant during the study and for 24 months after the last dose of the drug (see more details in Appendix B)
- To take 150 mg of GDC-0449 orally once daily with or without food and to swallow capsules whole. Capsules should not be opened or crushed.
- If a dose is missed, not to make up that dose but to resume dosing with the next scheduled dose.
- To notify the investigator immediately if they notice any changes with their health status or if they become pregnant.

2 Month, 4 Month, 5 Month, 7 Month, 8 Month, 9 Month, 10 Month and 11 Month Visit (+/- 7 Day Window)

- Continuance Criteria: patients will be released from study participation for the following reasons:
  - non-compliance with study procedures
  - development of a medical condition or taking a medication which would affect the study outcome, as covered in the exclusion criteria
  - disease progression or unacceptable toxicity of study drug, as assessed by the investigator
  - pregnancy
  - withdrawal of patient consent
  - protocol violation
  - lost to follow-up

- Review of Medical Records, if applicable
- Medical/Dental History update
- Concomitant Medications update
- Urine Pregnancy Test (if female of child bearing potential)
- Compliance with Study Drug
  - Compliance with study drug will be checked by counting the capsules that were returned to the site versus the capsules that were administered to patient at the end of the last visit. Any discrepancy will be documented in the patient's chart and in the drug accountability log. Study reminders regarding compliance will be reviewed with the patient in order to maximize the proper use of the study drug.
- Study Drug Dispense until next visit
- Adverse Events

Upon discharge from the clinic, specific instructions will be given to patients regarding the use of the medication, as well as adequate study drug supplies until their next visit. Patients will be instructed the following:

- Not to donate blood or blood products while receiving GDC-0449 and for at least 24 months after the last dose of the study drug.
- Not to get pregnant during the study and for 24 months after the last dose of the drug (see more details in Appendix B')
- To take 150 mg of GDC-0449 orally once daily with or without food and to swallow capsules whole. Capsules should not be opened or crushed.
- If a dose is missed, not to make up that dose but to resume dosing with the next scheduled dose.
- To notify the investigator immediately if they notice any changes with their health status or if they become pregnant.

#### **4.4.4 Phase 3: Post-Treatment (2 Years Follow-up):**

##### 7 Month, 1 Year and 2 Years Post-Treatment Visits (+/- 7 Day Window)

- Continuance Criteria: patients will be released from study participation for the following reasons:
  - non-compliance with study procedures
  - development of a medical condition or taking a medication which would affect the study outcome, as covered in the exclusion criteria

- disease progression or unacceptable toxicity of study drug, as assessed by the investigator
  - pregnancy
  - withdrawal of patient consent
  - protocol violation
  - lost to follow-up
- Review of Medical Records, if applicable
  - Medical/Dental History update
  - Concomitant Medications update
  - Urine Pregnancy Test (if female patient of child bearing potential)
  - Oral Cavity Assessment (soft & hard tissues, extraoral, head & neck)
  - Vital Signs (blood pressure, heart rate, temperature)
  - Panoramic Radiograph
  - Volumetric CT Scan (at 1 year and 2 year post-treatment visit)
  - Skin Examination for NBCCS-associated KCOT patients at 1 year post-treatment visit
  - Photographs of Skin Lesions, if applicable
  - Adverse Events
  - Study Completion/Discharge (at 2 year post-treatment visit)

During the 2 year post treatment phase and visits, patients will be reminded of the following:

- Not to donate blood or blood products while receiving GDC-0449 and for at least 24 months after the last dose of the study drug.
- Not to get pregnant during the study and for 24 months after the last dose of the drug (see more details in Appendix B)
- To notify the investigator immediately if they notice any changes with their health status or if they become pregnant

Should a patient decide to withdraw from the study or is discontinued by the investigator (see continuance criteria in phase 1 and 2), all efforts will be made to complete the discontinuation visit procedures and assessments (see Appendix A).

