## **2. STUDY OBJECTIVES**

### **2.1 Primary Objectives**

The primary objectives of the study are:

- a. To evaluate the efficacy of GDC-0449 in reducing KCOT size (shrinkage) in NBCCS-associated KCOT and sporadic KCOT patients following 6 to 12 months of ingestion of 150 mg/day, up to 1 year of treatment and up to 2 years of post-treatment follow-up.
- b. To evaluate the safety of this dose of GDC-0449 in these patients.

*Tumor response (reduction in tumor volume and shrinkage) will be measured by volumetric CT scan.*

*Time Frame: Efficacy will be assessed at 1 year and 2 years after the study medication is stopped. Patients will undergo evaluation for 3 years (up to 1 year of treatment and up to 2 years of post-treatment follow-up). All patients will participate in the assessment of the safety and tolerability of the study drug. Safety monitoring will capture risks related to study participation and adverse events related to the study drug.*

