### **Panoramic Radiograph and Volumetric CT Scan**

Tumor volume will be measured at baseline, and tumor response (reduction in tumor volume and recurrence) will be measured during the treatment phase and post-treatment phase by Panoramic Radiograph and Volumetric CT scan. The use of Panoramic Radiograph and Volumetric CT scan to measure the tumor volume are obtained for clinical assessment purposes only. No additional scans will be performed for research purposes. Disease progression during the treatment phase will be classified by an increase of at least 20%, with an absolute change greater than 5 mm in tumor size after 3 months of treatment. KCOTs grow within the bone. CT scan and panoramic radiograph are superior, with regard to sensitivity and specificity, in terms of evaluating bone involvement.

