The safety and efficacy of vismodegib in pediatric patients has not been established. Studies in animals indicate that oral Hh pathway inhibitors pose a substantial risk of developmental defects during the post-natal period, which includes irreversible effects on growing teeth or bones and male reproductive organs. The occurrence of premature epiphyseal fusion has been identified on routine pharmacovigilance through literature review and from serious adverse events (SAEs) reported in an Investigator Sponsored Trial (IST) of pediatric patients receiving vismodegib therapy. In some cases, fusion progressed after drug discontinuation.

In this study, the safety and efficacy of oral GDC-0449 in the management of NBCCS-associated KCOT and sporadic KCOT will be examined. The recommended dose is 150mg taken orally once daily until disease progression or until unacceptable toxicity. The capsule has a pink opaque body and a grey opaque cap with "150 mg" printed on the capsule body and "Vismo" printed on the capsule cap in black ink. It can be taken

with or without food and capsules should not be opened or crushed. If patients miss a dose, they will be advised not to make up that dose but instead to resume dosing with the next scheduled dose.

Pregnancy status prior to the initiation of GDC-0449 will be verified with a serum pregnancy test. Male and female patients will be advised of the risks of embryo-fetal death and severe birth defects and the need for contraception during and after treatment.

In addition, patients must agree not to donate blood or blood products during the study and for 24 months after discontinuation of vismodegib.

If a patient experiences unacceptable drug toxicity, he/she will be allowed a treatment break lasting for at least one month, up to three months. If the patient is unable to resume treatment after an 3 month treatment break, he/she will be discontinued from the study.

A potential risk of treatment of KCOT with vismodegib is disease progression, *i.e.* tumor growth. Participants will be closely monitored with clinical and radiographic examination for evidence of disease progression. The natural history of KCOTs is that the tumors grow and expand slowly relative to the proposed examination schedule. Therefore, it is highly unlikely that unanticipated growth in participants on vismodegib would be encountered.

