#### **4.5 Discontinuation of Protocol-Specified Therapy**

No dose reductions will be allowed in this study. Treatment with vismodegib may only be interrupted for up to:

- Two consecutive weeks if a patient becomes temporarily unable to swallow capsules
  
- Two consecutive weeks in case of an intolerable toxicity finding

A total up to eight weeks of dose interruptions (e.g., 4 x 2-week interruptions, 8 x 1-week interruptions, etc.) is allowed during the Treatment Phase.

Protocol-specified therapy may be discontinued for any of the following reasons:

- Progressive disease (PD)
  
- Unacceptable toxicity
  
- Patient election to discontinue therapy (for any reason)
  
- Physician's judgment

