## 4.6 Subject Discontinuation

Study subjects may be discontinued from the study for any of the following reasons:

- non-compliance with study procedures
- development of a medical condition or taking a medication which would affect the study outcome, as covered in the exclusion criteria
- disease progression or unacceptable toxicity of study drug, as assessed by the investigator
- pregnancy
- withdrawal of patient consent
- protocol violation
- lost to follow-up

Should a patient decide to withdraw from the study or is discontinued by the investigator, all efforts will be made to complete the discontinuation visit procedures and assessments (see Appendix A).

In the event that a subject becomes pregnant during the study, the subject will be withdrawn from the study immediately upon confirmation of pregnancy. These subjects will be required to return to the study site to undergo discontinuation visit assessments. In addition, any documented pregnancy will be tracked and followed through outcome.

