### **b. Efficacy Analysis**

#### **i. Primary Endpoint**

The effect of GDC-0449 will be evaluated (at a significance level of 5% and controlling the false discovery rate) using Wilcoxon signed rank tests to compare the mean KCOT volume at baseline to those acquired at 6, 12, 24,36 and 48 months. These comparisons will also be accomplished using paired t-tests.

ii. Subject population for this analysis. As a primary intention to treat (ITT) analysis, we will analyze data from all randomized subjects who complete Phase 1. For these analyses, Phase 1 values will be substituted for missing observations. Should more than 20% of the data be missing at any observation interval, analysis of that interval will be abandoned. Deviations from this plan, for example, emergent interest in the analysis of the all-treated or protocol-compliant subjects, will be transparently pursued and reported.

iii. Treatment of missing data. Two secondary effectiveness analyses will either carry the last observation forward into missing cells, or use maximum likelihood estimates of those values. We expect the best estimate of efficacy is likely to lie within the limits set by these conservative (ITT) and liberal (LOCF, ML) treatments of missing data.

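### Release from the study, not only from drug, for toxicity or progression removes the off-drug CT scans that the primary objective at 1 and 2 years depends on

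*Combined protocol and SAP*

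**What the plan says.** **Objective.** Section 2.1: "Efficacy will be assessed at 1 year and 2 years after the study medication is stopped".

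**Release.** Sections 4.4.3 and 4.4.4 carry the same list at every treatment and post-treatment visit: "Continuance Criteria: patients will be released from study participation for the following reasons", including "disease progression or unacceptable toxicity of study drug, as assessed by the investigator". Under Potential Risks to Participants (section 4.4), on toxicity: "If the patient is unable to resume treatment after an 3 month treatment break, he/she will be discontinued from the study".

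**Softer or different wording.** Section 4.6 is permissive: "Study subjects may be discontinued from the study for any of the following reasons". Section 4.5 names progression and unacceptable toxicity as reasons to stop therapy only: "Protocol-specified therapy may be discontinued for any of the following reasons".

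**Data after release.** Sections 4.4.4 and 4.6 promise efforts to complete a discontinuation visit, and Appendix A puts a volumetric CT there. Section 3.1 extends follow-up after withdrawal for an adverse event only until that event resolves or stabilises. Nothing schedules a later CT.

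**Progression.** The imaging part of section 4.4 defines it for the treatment phase only: "Disease progression during the treatment phase will be classified by an increase of at least 20" per cent, with an absolute-change condition. For the post-treatment phase it speaks of measuring recurrence and sets no threshold.

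**Analysis.** Section 4.8 b.i will "compare the mean KCOT volume at baseline to those acquired at 6, 12, 24,36 and 48 months". The primary analysis substitutes the baseline value for a missing one, secondary analyses use LOCF or maximum likelihood, and a time point with more than 20% missing is not analysed.

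**The concern.** The off-drug objective asks what happens to tumour volume once treatment ends. The patients who stop early for toxicity and the patients whose tumours regrow are both needed to answer it, and the release lists end their imaging. In Phase 3 no study drug is given, so release cannot protect anyone from it, and regrowth is what that phase is there to observe. A volume that was not scanned at one or two years off drug cannot be recovered by analysis. At stake is whether this part of the primary objective can be reported at all and, if it can, whether the figure describes all treated patients.

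**Working it through.** **1. The plan's own figure.** Section 4.8 b.v gives detectable changes of about 1.0 SD (n=10) and 0.68 SD (n=20), two-sided 5%, 80% power. A noncentral t calculation with n multiplied by 3/π (Wilcoxon efficiency, normal data) gives 1.026 and 0.678, so the figures reproduce. They allow for no loss.

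**2. Loss from toxicity release alone.** Adverse-event discontinuation rates come from section 1.3.1.1: 5/33 and 16/71 (Table 5), 178/500 (the large safety study) and 14/26 (the Gorlin syndrome trial). Expected missing = 20p. More than 20% of 20 means 5 or more, since 4/20 is exactly 20%. So P(abandoned) = P(X ≥ 5), X ~ Binomial(20, p). The last column is the detectable change if only measured patients were analysed, with n rounded to 17, 15, 13 and 9.

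| Rate p | Missing of 20 | Measured | P(abandoned) | Detectable, SD |
|---|---|---|---|---|
| 15.2% | 3.0 | 17.0 | 0.18 | 0.74 |
| 22.5% | 4.5 | 15.5 | 0.48 | 0.80 |
| 35.6% | 7.1 | 12.9 | 0.89 | 0.87 |
| 54% | 10.8 | 9.2 | 0.998 | 1.10 |

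**3. Adding release for regrowth, by year 2.** The documents give no regrowth rate for KCOT after vismodegib, so 20% to 40% of those who tolerate drug is an assumption. Measured = 20 × (1 − p) × (1 − r). At p = 15.2% this gives 13.6 to 10.2 patients and P(abandoned) 0.82 to 0.99. At 35.6% it gives 10.3 to 7.7, with P above 0.99.

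**4. If the time point is kept.** At most 4 of 20 are then missing. Illustration with assumed volumes: 16 measured patients stay at 50% of baseline, and the 4 released were last scanned at 50%.
- Released patients regrow to 120%: true mean (16×50 + 4×120)/20 = 64%, a 36% reduction. Baseline substitution: (16×50 + 4×100)/20 = 60%, a 40% reduction, too favourable.
- They regrow to 80%: true mean (16×50 + 4×80)/20 = 56%, a 44% reduction. Substitution still gives 40%, too unfavourable.
- LOCF from the 50% scan gives a 50% reduction in both cases.

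Substitution counts released patients as unchanged and hides growth beyond baseline. The direction of its error depends on the missing volumes.

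**5. Which time point.** Toxicity release affects both. Regrowth first seen on the 1-year off-drug CT is measured there. Before that, the only scheduled post-treatment image is the 7-month panoramic film, so selection on relapse falls mainly on year 2.

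**6. Timing.** For a patient who stops drug at month 6 and stays, follow-up counted from last dose (section 2.1) puts the CTs at 6 + 12 = 18 and 6 + 24 = 30 months. Counted from the end of the treatment phase (section 3.2), read as the 1 Year Visit, they fall at 24 and 36. Section 4.8 b.i counts from baseline.

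**The case against.** The strongest reply is that the plan limits the damage. Released patients are not dropped from the primary analysis, because baseline is substituted. The discontinuation visit includes a CT that LOCF can use. Reasons for loss are tabulated (section 4.8 a). The 20% rule stops a heavily depleted time point from being analysed. All of this stands, and it rules out several stronger readings.

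- A reader might infer that the trial would report lasting shrinkage when half its responders had relapsed. With half missing, section 4.8 would abandon the time point, so no such figure would be reported under the plan.
- A reader might infer that the off-drug results are a pure completer estimate, biased towards benefit. Substitution prevents the first, and step 4 shows that the direction is not fixed.
- A reader might take off-drug regrowth as certain to trigger release. Progression is defined only for the treatment phase, so this is left to the investigator.
- A reader might take early stoppers' scans as certain to miss the 24- and 36-month points. That holds only if follow-up runs from last dose, and section 3.2 can be read otherwise.
- A reader might quote 7 to 11 of 20 lost. That uses only the two higher rates; Table 5 implies about 3 to 4.5.

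It is also fair that section 4.6 is permissive and section 4.5 treats stopping therapy separately. But the visit-level lists are worded as mandatory, and no section keeps a released patient in imaging follow-up. The safeguards limit a misleading estimate; they do not supply the missing scans.

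**Conclusion.** The point holds. Followed as written, the visit-level release lists lose the 1- and 2-year off-drug volumes of patients released for toxicity or progression, and these volumes are part of the primary objective. About 3 to 11 of 20 patients would be affected by toxicity release alone, with a chance of about 0.18 to 0.998 that the time point is abandoned. The likelier harm, at the two higher rates, is an unanswered objective. If the time point is kept, the bias is of unknown direction.

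This assumes 20 treated patients, independent losses, rates carried over from other indications, and that every adverse-event drug discontinuation leads to release, as the visit-level lists direct. The year-2 figures also rest on the assumed 20% to 40% regrowth.

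**What to change.** 1. Reconcile Potential Risks to Participants (section 4.4), sections 4.4.3 and 4.4.4, and sections 4.5 and 4.6, so that stopping study drug is distinct from leaving the study. The limits on treatment breaks for toxicity also differ (one to three months under Potential Risks, two consecutive weeks in section 4.5). They affect who is released and must be reconciled by those responsible for the clinical rules.
2. Keep patients who consent on the existing Phase 3 visit and CT schedule after drug is stopped for any reason.
3. Remove progression and toxicity from the Phase 3 release list, and record off-drug regrowth as an outcome with its date.
4. Record any excision with its date. Section 4.1.1 accepts excision on progression or intolerance, and a later CT would measure surgery. Do not pool post-excision volumes as drug effect; analyse them separately or treat excision as an outcome event.
5. Reconcile the follow-up timing in sections 2.1, 3.2 and 4.8 b.i, and index the two follow-up comparisons to time since last dose.

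No dosing, stopping or other clinical rule changes. If released patients were still scanned, these two causes would add no missing data and the 0.68 SD figure would stand. The cost is protocol and consent wording, since the visits and CTs are already in Appendix A. Some patients will decline later visits. The statement in section 4.4 that scans are for clinical assessment, with none added for research, should be checked for consistency.

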### Phase II BCNS Study (SHH4685s)

The anti-BCC efficacy of vismodegib was tested in a randomized, double-blinded, placebo-controlled, Investigator-sponsored trial in Gorlin syndrome (BCNS) patients with surgically eligible BCCs [13-15]. Forty-one patients were randomized 2:1 to receive oral vismodegib (n=26) or placebo (n=15). After a mean follow up of 8 months (range, 1 to 15 months), the per-patient rate of new surgically eligible BCCs (SEBs) was lower with vismodegib than with placebo (2 vs. 29 cases per group per year, p<0.001), as was the size (percent change from baseline in the sum of the longest diameter) of existing clinically significant BCCs (–65% vs. –11%, p=0.003). In some patients, all BCCs clinically regressed. No tumors progressed during treatment with vismodegib. Patients receiving vismodegib routinely had Grade 1 or 2 AEs of loss of taste, muscle cramps, hair loss, and weight loss. Overall, 54% of patients (14 of 26) receiving vismodegib discontinued drug treatment due to AEs. At 1 month, vismodegib use had reduced the Hh pathway's target-gene expression in BCC cells by 90% (p<0.001) and diminished tumor-cell proliferation, but apoptosis was not affected. No residual BCC was detectable in 83% of biopsy samples taken from sites of clinically regressed BCCs. At the second pre-specified interim analysis, a data safety and monitoring board concluded that the pre-determined threshold for a significant difference between the two groups had been reached (p<0.0113), and the treatment with placebo in this arm was terminated. AEs reported in ≥10% of patients are summarized in Table 9 See the Vismodegib Investigator's Brochure and the U.S. package insert for additional details on nonclinical and clinical studies on vismodegib.

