#### **4.1.2 Exclusion Criteria**

Patients are excluded from participation if the following applies:

- Concurrent anti-tumor therapy;
- Completion of the most recent anti-tumor therapy (including Vismodegib) less than 4 weeks prior to the initiation of treatment (first study drug administration);
- Uncontrolled medical illness;
- Pregnancy or lactation; female patients who are planning to become pregnant for the duration of the study and 24 months post-treatment;
- Inability or unwillingness to swallow capsules;
- Any medical or psychological illness or condition preventing adequate consent;
- History of significant atherosclerotic disease, including the following:
  - Coronary artery disease (i.e., myocardial infarction within the past year or unstable angina);
  - Documented carotid atheroma;
- Known HIV infection;
- Current alcohol abuse;
- History of resistance to vismodegib (patients who previous received vismodegib for BCC and had no clinical response will be excluded).

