### **Dermatologic Assessments**

A thorough skin examination will be performed by a study investigator for NBCCS-associated KCOT patients at different time points (see Appendix A for more details). The purpose of this exam will be to identify any suspicious lesions. Patients with suspicious findings will be referred to a dermatologist as per standard of care. Photographs of the lesions will be taken and all findings will be recorded on the relevant CRF. Follow-up visits with a dermatologist will be conducted for patients with suspicious lesions as per standard of care. All findings by a dermatologist will be kept with the study records.

Any abnormal findings will be documented. Any abnormalities noted at the Baseline visit, may be reason to exclude a patient from the study. At the time of the first study drug administration or post-dose, should an adverse event be reported, the investigator will determine which safety assessments should be performed. All findings will be recorded on the respective CRF.

Any clinically significant signs or symptoms that are present at, or during the Baseline visit, and that worsen during or after study drug administration, will be recorded as adverse events on the adverse event CRF. Non-significant clinical abnormalities will also be recorded on the relevant CRF.

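### Starting an anti-tumor drug for a skin cancer in follow-up can end study participation, and the plan neither secures nor correctly labels the off-drug primary volumes that follow

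*Combined protocol and SAP*

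**What the plan says.** The visit lists in Sections 4.4.3 and 4.4.4 open with "Continuance Criteria: patients will be released from study participation for the following reasons", and one reason is "development of a medical condition or taking a medication which would affect the study outcome, as covered in the exclusion criteria". The list is repeated for every post-treatment visit, when patients are off study drug.

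The exclusion criteria it points to (Section 4.1.2) include "Concurrent anti-tumor therapy" and "Completion of the most recent anti-tumor therapy (including Vismodegib) less than 4 weeks prior to the initiation of treatment". Neither is limited to KCOT, and the term is not defined as local, topical or systemic.

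Section 4.6 gives the same reasons under a different verb: "Study subjects may be discontinued from the study for any of the following reasons".

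After release, only a discontinuation visit is planned. Appendix A marks a volumetric CT there. The off-drug CTs are scheduled at 1 and 2 years post-treatment, which are months 24 and 36 after a 12-month treatment phase. Section 2.1 makes efficacy at those times a primary objective, and Section 4.8.b tests those volumes against baseline. For missing values, Section 4.8.b substitutes the Phase 1 value. It drops an interval when more than 20% of its data are missing, and adds LOCF and maximum-likelihood analyses as secondary.

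**The concern.** NBCCS patients are prone to BCC, and the protocol expects this. It examines their skin at baseline, during treatment and at 1 year post-treatment, and refers suspicious lesions to a dermatologist. The KCOT case in Section 1.2 was an NBCCS patient who took vismodegib for his BCCs, and Section 4.1.2 foresees patients who have already had it for BCC. A drug started for BCC during follow-up is therefore a foreseeable event, and with vismodegib it is the very drug whose lasting effect on KCOT is being measured.

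The primary off-drug result then depends on which section a site follows. Under 4.4.4 the patient leaves and the analysis records no change from baseline. If the site uses the discretion in 4.6 and keeps the patient, the next CT enters the test as an off-drug volume although it was taken on a hedgehog inhibitor. The first path pulls the estimate toward no effect. The second, if the drug shrinks KCOT, pulls it toward lasting shrinkage. The NBCCS cohort is the one mainly exposed.

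**Working it through.** **Inputs.** 10 NBCCS and 10 sporadic patients (Section 3.1). Two-sided 5%, 80% power, detectable change of about 1.0 SD at n=10 and 0.68 SD at n=20 (4.8.b.v). Baseline substitution and the 20% limit (4.8.b.ii). The probability q that an NBCCS patient is released before the scan is not in the documents; it is assumed and varied.

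**1. The plan's own figure.** I used the noncentral t for a signed-rank test with normal data: effective size m = n × 3/π, df = m − 1, noncentrality d√m. Solving for 80% power gives d = 1.026 at n=10 and 0.678 at n=20. The stated figures reproduce. They assume that every patient is observed.

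**2. The 20% limit.** The documents do not say whether it applies by cohort or to all 20 patients.
- By cohort: 20% of 10 is 2, so 3 losses drop the interval.
- Pooled: 20% of 20 is 4, so 5 losses drop it.

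With X ~ Binomial(10, q), P(X ≥ 3) = 1 − Σ C(10,x) qˣ(1−q)¹⁰⁻ˣ over x = 0, 1, 2. At q = 0.20 this is 1 − (0.107 + 0.268 + 0.302) = 0.32. The pooled column is P(X ≥ 5) with the sporadic cohort complete.

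| Assumed q | By cohort, ≥3 of 10 | Pooled, ≥5 of 20 |
|---|---|---|
| 5% | 1% | <1% |
| 10% | 7% | 0.2% |
| 20% | 32% | 3% |
| 30% | 62% | 15% |

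**3. Below the limit.** With k of 10 values set to baseline and a true change of 1.0 SD, the estimated mean change is (10 − k)/10 SD. Power below is simulated for a single exact signed-rank test at 5%, with zeros dropped.

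| k filled | Mean change | Power |
|---|---|---|
| 0 | 1.0 SD | 0.78 |
| 1 | 0.9 SD | 0.69 |
| 2 | 0.8 SD | 0.61 |
| 3 | 0.7 SD | 0.57 |
| 4 | 0.6 SD | 0.35 |

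The rows for 3 and 4 apply only under the pooled reading; by cohort, the interval would already have been dropped. For the combined test at 0.68 SD, power is 0.80 with none filled and 0.69 with 4 of 20 filled.

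**4. If the patient is kept.** Each patient measured on restarted drug adds one tenth of that patient's change to the NBCCS cohort mean. Section 4.8 has no term that separates this value from an off-drug one. I put no error rate on this path, because the shrinkage on restarted drug and the measurement noise are not given.

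**The case against.** The strongest objection is one of scale. A reader might infer that most of the NBCCS cohort must be lost, because Section 1.3.1.1 reports that the rate of new lesions "was lower with vismodegib than with placebo (2 vs. 29 cases per group per year". Read as 29 per year in the placebo group of 15, this is 29/15 = 1.93 per patient-year, and 1 − exp(−2 × 29/15) = 98% of patients would have a new lesion within 2 years. The inference fails. The count is of surgically eligible lesions in patients selected for having them, excision is not a medication, and the approved use in Section 1.2 is confined to metastatic disease or to locally advanced disease with limits on surgery and radiation. Nothing in the documents gives the share who start a drug. At 5% or 10%, loss of the interval is unlikely.

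Nor can one say without qualification that such patients must be released. The rule covers only a medication that would affect the outcome, topical treatment is not clearly included, and Section 4.6 is permissive. Vismodegib itself is harder to argue away, since Section 4.1.2 names it as anti-tumor therapy and its effect on KCOT is the study question.

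It would also be wrong to say that Section 4.8 ignores released patients. It has baseline substitution, and the discontinuation-visit CT could be carried forward in the secondary LOCF analysis. Baseline substitution keeps all 20 patients, so its direct effect is a shift toward zero change, not a drift toward the sporadic cohort. What remains is that the primary value is a filled zero where a scan could have been taken.

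Finally, the dermatology text ("Follow-up visits with a dermatologist will be conducted for patients with suspicious lesions as per standard of care") does not contradict the release rule. It covers referral and filing, and is silent on drug treatment and continued participation. Concomitant-medication changes are already recorded throughout, so no new data stream is needed.

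**Conclusion.** The concern holds in a limited form. The release wording in 4.4.3 and 4.4.4 conflicts with 4.6. On either reading, an NBCCS patient who starts an outcome-affecting anti-tumor drug in follow-up has no sound off-drug primary value: it is either filled as zero change or measured on restarted drug without a label.

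The size is unknown, because the rate of drug starts is unknown. With 10 patients per cohort, one or two releases lower signed-rank power at the planned 1.0 SD from 0.78 to 0.69 or 0.61. Whether the NBCCS interval is likely to be dropped depends on an assumed release rate of about 20% or more and on the 20% limit being applied by cohort. Under the pooled reading that outcome is unlikely at such rates. The power figures assume normally distributed changes and one unadjusted test at 5%.

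**What to change.** - Reconcile the mandatory wording in 4.4.3 and 4.4.4 with the permissive wording in 4.6 and with the anti-tumor items in 4.1.2, and define which therapies are meant. Which on-treatment rule is right is for the investigators; this point asks for no change there beyond consistency, and none to BCC care.
- For the post-treatment phase only, separate starting other therapy from leaving the study, so that the 1- and 2-year CTs already in Appendix A are still collected from patients who consent. This adds no scan to the schedule. Section 4.4 says scans are for clinical assessment only, so the wording should be checked against that statement.
- In 4.8.b, use volumes as observed after local BCC treatment. Report volumes taken after any systemic hedgehog inhibitor is restarted separately, and do not count them as off-drug response. Take start dates from the existing concomitant-medication record.
- State in 4.8.b whether the 20% limit applies per cohort or to all 20 patients.

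The cost is protocol wording, one extra summary, and a slightly smaller set of clean off-drug volumes.
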